Hemostatic effect is determined by dose of oxymetazoline instilled by the surgeon.

Methods:

Thirty patients of [name] who will undergo functional endoscopic sinus surgery, turbinate surgery or adenoidectomy and are anticipated to receive oxymetazoline-soaked pledgets for hemostasis will be enrolled.

Patients ages 2 through 18 yrs. will be enrolled if they are scheduled for

- 1) Functional endoscopic sinus surgery (ten patients)
- 2) Turbinate reduction (with or without tonsillectomy and/or adenoidectomy) (ten patients)
- 3) Adenoidectomy (ten patients)

Patients will be excluded if they have been treated with oral decongestants or antihistamines within 24 hours of surgery, are taking anticoagulants, have a history of nasal trauma within past 3 months, have a history of epistaxis within past 3 months, have a history of hypertension or cardiac disease, or are allergic to oxymetazoline.

There will be no change in the conduct of the general anesthetic care related to the study protocol. Our usual practice will be followed. For premedication, midazolam (0.5 mg/kg to a maximum of 15 mg) will be administered 15-45 minutes prior to the procedure at the discretion of the attending anesthesiologist. An inhalation induction with sevoflurane or an intravenous induction with propofol will be performed by the attending anesthesiologist and titrated to attempt to maintain the bispectral index (BIS) between 40 and 60 to ensure adequate and similar depth of anesthesia. It will not be considered a protocol violation if the BIS is not maintained at this level. Fluid will be administered to

attempt a total of 15 ml/kg for procedures less than 1 hr or maintenance plus replacement for procedures greater than 1 hr. It will not be considered a protocol violation if this amount of fluid is not infused.

Blood pressure and heart rate and will be recorded at 5 min intervals until discharge from PACU or final blood draw, whichever comes first.

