The surgeon will place oxymetazoline-soaked pledgets according to usual practice. [name] will make two different observations to assess the amount of bleeding and ease of hemostasis (10)

- 1) A four point scale to record subjective bleeding following removal of pledgets

- 0= none, 1= minimal/restricted, 2=moderate/diffuse ooze, 3=severe/brisk
- 2) A six point scale to assess ease of hemostasis
1=very easy, 2=easy, 3=usual, 4=some effort required, 5=difficult, 6=extremely difficult

Blood pressure and heart rate and will be retrieved from EPIC for analysis

Prior to the study Drs. [name] & [name] determined that 10 pledgets in 15 ml of oxymetazoline (1.5 ml per pledget) provided the necessary amount of oxymetazoline for clinical use. The number of pledgets placed will be recorded at the time of insertion. If placement is separated by greater than five minutes, then this will be recorded as a separate event. The volume at each time point and the total dose will be recorded. Age-matched, procedure matched control patients not receiving oxymetazoline will be used for comparison. We will do a retrospective chart review of the control patients for hemodynamic parameters.

Statistical Analysis:

Compare the incidence of hypertension using systolic blood pressure and mean arterial pressure criteria using age adjusted normative tables

Compare the incidence of bradycardia defined as HR < 60 bpm, or tachycardia defined as HR>100

Compare the use of vasodilators for the treatment of hypertension

Compare the use of atropine/glycopyrrolate for the treatment of bradycardia

Compare the volume of oxymetazoline instillation and hemodynamic changes

Measure the serum level of oxymetazoline at approximately 5 (3-6 min), 10(8-12 min), 20(18-22 min), 45 (30-60 min), 90 (75-120 min) and 150 (135-240 min) minutes using the protocol specified above.

Compare the degree of bleeding and the ease of hemostasis using the subjective rating scale by the single surgeon observer.

All demographic and parametric data will be presented as mean (\pm SD). Normally distributed interval data will be analyzed using unpaired t-test. Nominal or ordinal data will be analyzed using Chi-squared contingency table or a Fisher's exact test with Yates correction factor. A $P < 0.05$ will be used to express statistical significance.

REFERENCES:

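### Controls are matched on age and procedure, but every named test treats the groups as independent, which costs power if outcomes are correlated within matched sets

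*Combined protocol and SAP*

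**What the plan says.** The Methods section enrols thirty treated children aged 2 to 18, ten for each of three procedures. The comparison group is described near the end of Methods: "Age-matched, procedure matched control patients not receiving oxymetazoline will be used for comparison". Its data come from records: "We will do a retrospective chart review of the control patients for hemodynamic parameters".

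The Statistical Analysis section lists comparisons of the incidence of hypertension, of bradycardia or tachycardia, of vasodilator use and of atropine/glycopyrrolate use. It then gives two rules for all data: "Normally distributed interval data will be analyzed using unpaired t-test" and "Nominal or ordinal data will be analyzed using Chi-squared contingency table or a Fisher's exact test with Yates correction factor". The significance threshold is P < 0.05.

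No paired, conditional, stratified or covariate-adjusted method is named. The document does not say whether matching is child by child or by group, how many controls there are, what the ratio is, or how close in age a match must be.

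**The concern.** Matching on prognostic factors is meant to make the comparison groups alike and to gain precision. The precision is gained only if the analysis uses the matching. A test for independent groups adds the two group variances and ignores the covariance that matching creates. When that covariance is positive, the standard error of the difference is too large, the nominal 5% test runs below 5%, and real differences are missed more often.

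This bears on the primary objective, the hemodynamic effect. The working hypothesis is that oxymetazoline raises blood pressure, so an avoidably insensitive test makes a real effect harder to see with only thirty treated children.

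**Working it through.** **The plan's own figure.** There is no power calculation, event rate, SD, correlation or number of controls to reproduce. The only figure is the treated sample, 10 + 10 + 10 = 30.

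**Assumptions, none from the documents.** 30 controls matched 1:1, two-sided 5% level, and the incidences and correlations shown below.

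**Step 1: standard error.** With common variance σ², n pairs and within-pair correlation ρ on the outcome scale:
- the unpaired test uses SE = σ√(2/n);
- the true SE of the difference is σ√(2(1 − ρ)/n);
- the ratio is 1/√(1 − ρ).

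The true size of a nominal 5% large-sample test is 2·P(Z > 1.96/√(1 − ρ)).

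| ρ | SE ratio | True size |
|---|---|---|
| 0 | 1.00 | 5.0% |
| 0.2 | 1.12 | 2.8% |
| 0.3 | 1.20 | 1.9% |
| 0.5 | 1.41 | 0.6% |

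**Step 2: binary outcomes, power.** This is an exact enumeration of the paired 2×2 table for 30 pairs. Pairs come from a latent bivariate normal. For 35% v 10%, latent correlations of 0.3 and 0.5 are 0.15 and 0.25 on the outcome scale.

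| 35% v 10%, latent correlation | Fisher | Exact McNemar | Chi-squared, uncorrected | Mid-P McNemar |
|---|---|---|---|---|
| 0 | 55% | 52% | 66% | 62% |
| 0.3 | 55% | 59% | 67% | 69% |
| 0.5 | 55% | 65% | 68% | 75% |

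The fair comparison is like with like. Exact against exact, pairing adds about 4 points at 0.3 and 10 at 0.5. Mid-P against uncorrected chi-squared, it adds about 2 and 7. Setting mid-P McNemar against Fisher would give 15 to 21 points, but much of that comes from the mid-P: at zero correlation mid-P is already 8 points above Fisher (62.3% v 54.5%).

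**Step 3: size in the same setting.** With 20% in both groups, Fisher's size is 2.2%, 1.3% and 0.7% at latent correlations 0, 0.3 and 0.5. Exact McNemar's is 2.2%, 1.9% and 1.6%. Discreteness alone brings Fisher to 2.2%; the further fall is due to ignoring the pairing.

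**Step 4: other settings.**
- Rare events, 15% v 3%, latent correlation 0.3 to 0.5: Fisher 13.5% to 12.3%, exact McNemar 15.3% to 15.1%. Little is gained.
- A larger contrast, 50% v 20%, with outcome-scale ρ of 0.2 to 0.5: Fisher 61-63%, exact McNemar 68-92%.
- An interval outcome with a 0.5 SD difference (40,000 simulations): unpaired t 48% and paired t 55% at ρ = 0.2; 47% and 76% at ρ = 0.5. At ρ = 0 the order reverses slightly, 48% v 47%.

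**Step 5: where correlation is likely.** The heart-rate outcomes use fixed cut-offs at every age from 2 to 18. Heart rate varies with age over that range, so two children of the same age tend to fall on the same side of a cut-off. Hypertension is judged against age-adjusted norms, which removes much of what age matching would contribute; procedure may still contribute.

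**The case against.** The document never says that each treated child has an individual partner. Its wording also fits frequency matching, under which McNemar and the paired t-test do not apply. This stands, and it is why the matching must be defined before a test is chosen. It does not rescue the plan: frequency matching calls for an analysis that accounts for procedure and age, and none is named.

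The power loss is conditional. It needs positive within-set correlation, for which there is no figure, and near zero a paired test gains nothing. This also stands. So does the point that no interval outcome is listed explicitly as treated versus control, so the t-test figures illustrate a general rule and attach to no named endpoint.

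Three stronger readings are tempting, and the documents do not support them:
- A reader might infer that the planned tests produce false positives. With positive correlation they err the other way.
- A reader might infer that the reported spread will be wrong. The plan reports group means with SDs, and pairing does not change a group SD. Only the standard error or confidence interval of the difference is affected.
- A reader might infer a loss of 15 to 21 points of power from mid-P McNemar against Fisher. Much of that gap is the mid-P and not the pairing.

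**Conclusion.** The point holds in a conditional form. Controls are selected by age and procedure, the named tests assume independent groups, and neither individual nor frequency matching makes them fit. If outcomes are positively correlated within matched sets, the analysis is conservative and gives up power. In the main illustration, pairing alone is worth about 4 to 10 points against Fisher. It is worth more where correlation or the contrast is larger, and almost nothing for rare events or near zero correlation.

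These sizes rest on an assumed 1:1 ratio and on assumed incidences and correlations. The point is strongest for the heart-rate outcomes and weaker for hypertension. Because the error does not inflate false positives, the severity is minor to moderate.

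**What to change.** 1. In Methods, state whether matching is individual or by frequency, with the ratio, the age tolerance and the number of controls. Record a matched-set ID when controls are selected, since it may be hard to reconstruct later.
2. In Statistical Analysis, replace the independent-group tests for treated-versus-control comparisons.
   - **Individual matching:** Incidences will be compared within matched sets, with a paired risk difference, its 95% CI and a McNemar test (exact or mid-P, chosen in advance), or by conditional logistic regression if a set has more than one control. Any interval outcome compared between treated and control children will be analysed with a paired t-test or a mixed model with a matched-set effect.
   - **Frequency matching:** stratify by procedure and adjust for age.

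The cost is one ID variable and a few sentences. If the matching proves weak, the paired analysis loses a few degrees of freedom: about 1 point of power for the t-test at zero correlation in the illustration above, and about 2 points for exact McNemar against Fisher.

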INVESTIGATORS: [name] MD, MBA; [name] MD; [name] MD; [name], BSN, RN, CCRC

Title: Prospective Hemodynamic and Pharmacokinetic Analysis of Oxymetazoline Absorption during Functional Endoscopic or Turbinate Reduction Surgery or Adenoidectomy.

Background and Significance:

Oxymetazoline is an α -adrenergic agonist that is commonly used as a topical sympathomimetic agent in over-the-counter decongestant sprays. Its vasoconstrictive action on the blood vessels defines its clinical utility as both a decongestant and a topical hemostatic agent(1). It is used extensively by otolaryngologists for functional endoscopic sinus surgery (FESS), turbinate surgery, and adenoidectomy to produce vasoconstriction. Riegler et al. compared cocaine 4%, phenylephrine 0.25%, and oxymetazoline 0.05% for nasal vasoconstriction in pediatric patients undergoing functional endoscopic sinus surgery (2), Children who were treated with oxymetazoline had less bleeding and improved visualization compared with the other two vasoconstrictors. Heart rate decreased, but blood pressure was unchanged during the first ten minutes after application. However, the authors did not determine the cumulative dose of oxymetazoline. Although there is generally limited vascular absorption, when administered in larger doses, uptake of oxymetazoline can lead to significant systemic hemodynamic effects, most commonly hypertension related to its action on the α -adrenergic receptors of the smooth muscle of the vasculature that results in vasoconstriction. Furthermore, when used in even larger doses in young children, oxymetazoline can activate central adrenergic receptors and lead to serious adverse effects including cardiovascular instability, respiratory depression, and neurologic complications, which may be potentially life-threatening (3-6) In the operating room, this reflex bradycardia may not always occur because general anesthetics, particularly volatile anesthetics, attenuate the baroreceptor response. Bradycardia may also be a consequence of the direct action of oxymetazoline on central α adrenergic receptors in the locus ceruleus and central vasomotor areas of the brainstem. Our institution recently reported a case of oxymetazoline induced postoperative hypertension in a three year old child following inferior turbinate reduction and adenoidectomy. (7)

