Giannakopoulos studied the cardiovascular effects and pharmacokinetics of an intranasal 3 percent tetracaine/0.05 percent oxymetazoline spray at two different dose levels in adult dental patients. (8) A small decrease in heart rate and a small increase in diastolic blood pressure was noted. Serum levels of oxymetazoline were measured and a half-life of 1.72 to 2.32 hours was noted. No similar pharmacokinetic studies have been reported in children. Latham and Jardine reported oxymetazoline-induced hypertension in a 4-year-old child. (9) They also sought to investigate alterations in the amount of medication delivered based on the delivery method. There was up to a 75-fold increase in the volume of medication administered when the bottle was held inverted. Squeezing the bottle in the upright position resulted in a mist with the delivery of $28.9 \pm 6.8 \mu\text{l}$ of fluid. The amount delivered was effort independent. When the bottle was inverted and squeezed, the volume administered was effort dependent.

Current practice at NCH is to soak nasal pledgets with full strength oxymetazoline and insert a varying number of pledgets on the nasal turbinates or into the sinuses for hemostasis, or on the adenoid bed.

This proposed study will assess the hemodynamic effects and measure the systemic absorption of topically applied oxymetazoline in patients undergoing functional endoscopic sinus surgery, turbinate surgery, or adenoidectomy.

Specific Aims/Objectives:

The primary objective is to determine the perioperative hemodynamic effect of oxymetazoline applied topically for vasoconstriction in patients undergoing functional endoscopic sinus surgery, turbinate surgery or adenoidectomy using blood pressure and heart rate intraoperatively (OR) and postoperatively (PACU) until discharge from phase 1 of the PACU.

A secondary objective is to measure the plasma concentrations of oxymetazoline at discrete time periods from instillation and correlate with hemodynamic effects, as well as determine the rate of decline in levels as a function of time.

A secondary objective is to assess the degree of bleeding and ease hemostasis rated by a single observer to minimize variability.

Hypotheses:

Instilled oxymetazoline causes an increase in blood pressure in the intraoperative and postoperative period and, though absorption is rapid and variable, effects are related to serum level of oxymetazoline.

The decline in hemodynamic effect and serum levels is a function of time.

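### Controls are chosen only on age, procedure and absence of oxymetazoline, so the rule admits children with the hypertension or cardiac disease that bars exposed patients, or children given another vasoconstrictor, and can bias the comparison

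*Combined protocol and SAP*

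**What the plan says.** Controls first appear at the end of Methods, just before Statistical Analysis: "Age-matched, procedure matched control patients not receiving oxymetazoline will be used for comparison". The next sentence gives the data source: "We will do a retrospective chart review of the control patients for hemodynamic parameters". No further criterion for controls appears anywhere in the document.

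Eligibility comes earlier in Methods and is written around enrolment. The thirty study patients are those who "are anticipated to receive oxymetazoline-soaked pledgets for hemostasis will be enrolled", and the procedure list opens with "Patients ages 2 through 18 yrs. will be enrolled if they are scheduled for". The exclusions follow directly: "Patients will be excluded if they have been treated with oral decongestants or antihistamines within 24 hours of surgery, are taking anticoagulants", then recent nasal trauma or epistaxis, and finally those who "have a history of hypertension or cardiac disease, or are allergic to oxymetazoline".

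Two statements in Background and Significance bear on who the controls might be. One describes the site: "Current practice at NCH is to soak nasal pledgets with full strength oxymetazoline". The other describes a cited study in sinus surgery that "compared cocaine 4%, phenylephrine 0.25%, and oxymetazoline 0.05% for nasal vasoconstriction in pediatric patients".

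Statistical Analysis lists comparisons of hypertension, bradycardia and tachycardia incidence, and of the drugs used to treat them. The tests are an unpaired t-test and chi-squared or Fisher's exact tests. No covariate is named.

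**The concern.** The exposed children are screened for conditions that affect blood pressure and heart rate. The controls, on the text as written, are not. Blood pressure and heart rate are the primary objective, so the gap falls on the outcomes that matter most.

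Because oxymetazoline is usual practice at this site, a child who did not receive it differs in some way from one who did. One plausible reason is that the clinicians avoided the drug because of hypertension or cardiac disease, which are the conditions that keep a child out of the exposed group. Another possibility is that a different vasoactive agent was used. Either kind of child meets the control rule.

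The protocol's background is largely about oxymetazoline-induced hypertension, including a case at the same institution. In that setting, a finding of no difference that arose from hypertensive controls would be the costly error.

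**Working it through.** The plan gives no power, effect size, event rate, standard deviation or number of controls, so there is no stated figure to reproduce. The first step compares the two rules. The others are illustrations on stated assumptions.

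**Step 1. Criteria side by side.**

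| Criterion | Exposed (enrolled) | Controls (chart review) |
|---|---|---|
| Age | 2 to 18 years | matched |
| Procedure | three types, ten each | matched |
| Oxymetazoline | anticipated | not received |
| Hypertension or cardiac disease | excluded | not stated |
| Anticoagulants | excluded | not stated |
| Oral decongestant or antihistamine within 24 h | excluded | not stated |
| Nasal trauma or epistaxis within 3 months | excluded | not stated |
| Other vasoconstrictor | not stated | not stated |

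Matching on age and procedure does not balance any of the four disease and drug exclusions.

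**Step 2. Dilution by another agent (continuous outcome).** Assumptions: 30 exposed (from Methods), 30 controls (not in the plan), two-sided alpha 0.05 (the plan gives 0.05 but not the sidedness), unpaired t-test, and another agent with the same pressor effect as oxymetazoline.

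- The effect detectable with 80% power is d = 0.736 SD.
- If k of 30 controls had the other agent, the expected difference is d × (1 − k/30). The standard deviation is held fixed.
- k = 2: 0.736 × 28/30 = 0.687, power 74%.
- k = 3: 0.736 × 27/30 = 0.662, power 71%.
- k = 5: 0.736 × 25/30 = 0.613, power 65%.
- k = 10 (every sinus-surgery control): 0.736 × 20/30 = 0.49, power 46%.

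The last line is a worst case. If all ten had an agent with half the effect, the factor is 1 − (10 × 0.5)/30 = 25/30, and power is again 65%.

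**Step 3. Hypertensive controls (incidence).** One control counted as hypertensive, in place of one who would not have been, adds 1/30 = 3.3 percentage points to control incidence overall, or 1/10 = 10 points within a ten-child procedure group. These are maxima, because a child with a history of hypertension need not meet the perioperative criterion, and the child replaced might have met it.

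**Step 4. The same in terms of rates.** Assume true hypertension rates of 40% exposed and 10% in eligible controls, 30 v 30, and 60% in controls with prior hypertension. With a share f of such controls, the control rate is (1 − f) × 10% + f × 60%.

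- f = 0: 10%, difference 30 points, power 78%.
- f = 10%: 15%, difference 25 points, power 59%.
- f = 20%: 20%, difference 20 points, power 39%.
- f = 30%: 25%, difference 15 points, power 23%.

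All the rates and shares in this step are assumptions.

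**The case against.** The strongest reply is that silence is not bias. The exclusion sentence speaks of patients generally, and a careful chart reviewer might apply it to controls. Nothing shows that any unsuitable child would be chosen. This stands as far as it goes: the documents permit such controls but do not show that they will occur. It does not remove the point, because the exclusion sentence sits with the enrolment criteria, the controls are not enrolled, and the control rule is otherwise complete as stated.

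A reader might infer that sinus-surgery controls at this site probably received cocaine or phenylephrine. The documents do not support that. Those agents appear only as arms of one cited study, and no other agent is described as site practice.

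A reader might also infer that the bias always runs toward no effect. That is not supported either. No passage says that topical cocaine or phenylephrine raises blood pressure, cardiac disease need not raise it, and allergy to oxymetazoline has no stated link to it. For heart rate the direction depends on the agent or disease. Children may also have gone without oxymetazoline because little bleeding was expected or by surgeon's choice.

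Finally, not every analysis is exposed. Relating instilled volume or plasma concentration to hemodynamic change does not need controls.

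**Conclusion.** The concern holds in a limited form. As written, the rule can set exposed children screened for hypertension and cardiac disease against unscreened controls, and it allows another vasoactive agent in those controls. The planned tests are unadjusted and cannot repair this. The omission is certain, but how often it would matter is not known from the documents.

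The direction can be argued only for pre-existing hypertension, which would most likely raise the control hypertension rate and mask an oxymetazoline effect. The figures above rest on an assumed 30 controls and assumed effects or rates. They show that a few affected controls cost modest power under an equal-effect agent (80% to about 71% with three) and that only the extreme case brings it to 46%. The plan should be changed before charts are selected.

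**What to change.** Amend the control sentence in Methods so that, besides matching on age and procedure and having had no oxymetazoline, controls must:

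- meet every enrolment exclusion that can be read from the chart, and at minimum have no history of hypertension or cardiac disease;
- have received no other topical or injected vasoconstrictor during the procedure.

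Record any such vasoconstrictor use for each chart screened. If too few controls remain, report the children given another agent as a separate group and do not pool them with the untreated controls.

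The cost is a few sentences and one more screen in a chart review that is already planned. There are three downsides. The control pool will shrink, which may matter at a site where oxymetazoline is usual. Some exclusions, such as antihistamine use in the previous 24 hours or recent epistaxis, may be poorly charted. Selection by the surgeon's reason for withholding oxymetazoline would remain and should be stated as a limitation.

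### No treated-versus-control comparison uses the child's own blood pressure or heart rate before pledget placement, so a starting difference from chart-review controls can be taken for a drug effect or can hide one

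*Combined protocol and SAP*

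**What the plan says.** Under Hypotheses the protocol states: "Instilled oxymetazoline causes an increase in blood pressure in the intraoperative and postoperative period". The primary objective concerns blood pressure and heart rate in the operating room and in recovery.

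The comparison group is described in Methods: "Age-matched, procedure matched control patients not receiving oxymetazoline will be used for comparison", followed by "We will do a retrospective chart review of the control patients for hemodynamic parameters". The number of controls and the matching ratio are not given. For the source of the readings, Methods says "Blood pressure and heart rate and will be retrieved from EPIC for analysis". Readings are taken every 5 minutes. An end to recording is stated, but no start.

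Statistical Analysis lists these comparisons that are possible against controls:

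- "Compare the incidence of hypertension using systolic blood pressure and mean arterial pressure criteria using age adjusted normative tables"
- incidence of heart rate below 60 or above 100
- use of vasodilators
- use of atropine or glycopyrrolate

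One further item reads "Compare the volume of oxymetazoline instillation and hemodynamic changes". Controls have no instilled volume, so this is a dose relation among treated children, and no starting value for the changes is defined.

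The tests are generic: "Normally distributed interval data will be analyzed using unpaired t-test" and "Nominal or ordinal data will be analyzed using Chi-squared contingency table or a Fisher's exact test with Yates correction factor". No covariate, blood-pressure variable, time point or summary of the 5-minute series is named.

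**The concern.** A rise in blood pressure is a statement about change, and the natural reference is the same child before the pledgets go in. No control comparison in the plan uses that reference. A child who was already above the age norm before instillation counts as hypertensive in the same way as one who rose afterwards.

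In a randomised trial, starting levels would balance on average. Here the controls are historical and matched on two factors only. Matching on age and procedure does not equalise starting pressure. Methods leaves premedication to the anesthesiologist's discretion, allows inhalational or intravenous induction, and does not treat departures from the depth-of-anesthesia or fluid targets as violations. Treated and control children of the same age and procedure can therefore start at different levels. An unadjusted comparison would then mix that difference with the drug effect, in either direction, on the study's main hypothesis.

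**Working it through.** **Figures in the plan.** Thirty treated patients, 10 + 10 + 10 = 30 by procedure (Methods), and a significance level of 0.05 (Statistical Analysis). The plan gives no power, effect size, SD, event rate or number of controls, so there is no power figure to reproduce.

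**Assumed for illustration.** 30 controls; two-sided test; normally distributed blood pressure, scaled to SD 1; one reading per child; starting gap g = 0.3 to 0.5 SD; correlation r = 0.3 to 0.7 between the pre- and post-instillation readings; true shift 0.7 SD where an effect is assumed.

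**Formulas.**
- Unpaired t-test: standard error √(2/30) = 0.258, 58 degrees of freedom.
- ANCOVA: standard error √((1 − r²) × 2/30), 57 degrees of freedom.
- Rejection probabilities come from the noncentral t distribution, with noncentrality = expected difference / standard error.

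**Step 1: no drug effect, gap carries over as g × r.**
- t-test, smallest case: 0.3 × 0.3 = 0.09; 0.09/0.258 = 0.35; rejects 6%.
- t-test, largest case: 0.5 × 0.7 = 0.35; 0.35/0.258 = 1.36; rejects 27%.
- ANCOVA: expected bias g × r − r × g = 0; rejects about 5%. This follows from the assumed model and is not independent evidence for the method.

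**Step 2: no drug effect, gap persists in full.**
- t-test: 0.3/0.258 = 1.16, rejects 21%; 0.5/0.258 = 1.94, rejects 48%.
- ANCOVA, bias g × (1 − r). Smallest: 0.3 × 0.3 = 0.09, standard error √(0.51 × 2/30) = 0.184, ratio 0.49, rejects 8%. Largest: 0.5 × 0.7 = 0.35, standard error √(0.91 × 2/30) = 0.246, ratio 1.42, rejects 29%. Simulation, which allows for the extra variance caused by the baseline imbalance itself, gives 27% for the largest case.

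**Step 3: true shift 0.7 SD, treated children start lower by g.** With no gap, 0.7/0.258 = 2.71 and t-test power is 76%.
- Carry-over: the net difference is 0.7 − 0.09 = 0.61 down to 0.7 − 0.35 = 0.35, and t-test power is 64% down to 27%. ANCOVA keeps 76%-95% (simulation).
- Full persistence: the net difference is 0.4 or 0.2, and t-test power is 33% or 12%. ANCOVA has 27%-89%.

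**Step 4: true shift 0.7 SD, no gap.**

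| Analysis | Power |
|---|---|
| Unpaired t-test | 76% |
| ANCOVA, r = 0.3 / 0.5 / 0.7 | 80% / 87% / 96% |
| Fisher, control hypertension rate 5% / 10% / 20% | 15% / 31% / 42% |

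For the Fisher row, the treated rate is p1 = 1 − Φ(z(1 − p0) − 0.7), which gives 17.2%, 28.0% and 44.4%. Power is by full enumeration. This row matters only if incidence at a single reading were the sole comparison made.

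**Step 5: a brief effect.** This was simulated with 24 five-minute readings per child and a peak of 1.5-2 SD with a half-life of 10-15 minutes, all assumed. ANCOVA has 26%-41% power on the whole-window mean and 64%-96% on the per-patient peak; Fisher on any hypertensive episode has 16%-37%. With no effect but 24 readings in one group and 16 in the other, ANCOVA on the peak rejects in 14%-19%.

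**The case against.** The best defence is that the plan is short, not that it chooses yes/no outcomes. It retrieves hemodynamic parameters for controls, presents parametric data as mean and SD, and assigns interval data to a t-test. Blood pressure is an obvious variable for that sentence to cover. This stands. A reader might infer that the study is confined to incidences and so gives up most of its power, but the documents do not support that. The Fisher figures in Step 4 are therefore secondary.

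It is also fair to say that hypertension incidence is a sensible outcome. The background is built on case reports of oxymetazoline-induced hypertension in children, and age norms deal directly with an age range of 2 to 18, which a raw mean does not. A reader might infer that incidence should give way to a continuous outcome. That is a trade-off for the sponsor, not an error in the plan.

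Confounding is partly handled by matching, and anesthetic care of enrolled patients follows usual practice with a depth target. This helps, but neither measure equalises starting pressure. The 5-minute readings may well include pre-instillation values; the plan does not say that any are used.

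Finally, the gap of 0.3-0.5 SD has no source in the documents. That is correct: the calculation shows what such a gap would do, not that one exists.

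**Conclusion.** The point holds as a gap in the analysis. The hypothesis is a rise in blood pressure, the controls are non-randomised, and no treated-versus-control comparison uses the child's own pre-instillation value. The only test for continuous data is unadjusted and ignores the matching.

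If groups of 30 started 0.3-0.5 SD apart, the unadjusted t-test would give a false positive in 6%-27% or 21%-48% of studies, depending on whether the gap fades or persists, against a nominal 5%. A gap in the other direction could cut power from 76% to between 12% and 64%. Every input except the 30 treated patients and the 0.05 level is assumed.

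Two limits apply. Baseline adjustment reduces the confounding but does not remove it: with a persistent gap, ANCOVA still rejects a true null in about 8%-29%. A reader might also infer that any t-test or ANCOVA on continuous pressure restores power. That fails for a whole-window mean when the effect is brief (Step 5), and the documents do not establish how long the effect lasts in children.

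**What to change.** Keep the listed incidence and treatment-use comparisons. Add one named treated-versus-control comparison of continuous systolic or mean arterial pressure:

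- State one per-patient summary (mean or peak) in advance, over a post-instillation window of the same length in both groups. The Objectives end observation at discharge from phase 1 recovery; Methods ends it at recovery discharge or the last blood draw, whichever is earlier. Choose one.
- Analyse by ANCOVA, or by a mixed model on the individual readings. Adjust for the last pre-instillation reading and for age and procedure or the matched set. In controls, use the reading at a pre-stated surgical index time.
- State which comparison, this one or hypertension incidence, is the main test of the hypothesis.
- Report that residual confounding remains because controls are not randomised.

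No new patients or visits are needed, and the readings already come from the electronic record. The cost lies in the details. The control index time must be constructed from charts and may be misaligned. Pre-instillation readings must be confirmed in both groups, since no start of recording is stated. Variable recovery stay limits the common window. A mean dilutes a brief peak, and a peak is biased if the groups have different numbers of readings.
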